### **8.3.8.2 Hypersensitivity Reactions**

Hypersensitivity reactions will be assessed according the Common Terminology Criteria for Adverse Events of the National Cancer Institute (CTCAE v5.0), see [Table 8-1](#).

**Table 8–1: Common Terminology for Adverse Events Related to Immune System Disorders (CTCAE v-5.0)**

Adverse Event	Immune system disorders				
	Grade				
	1	2	3	4	5
Allergic reaction	Systemic intervention not indicated	Oral intervention indicated	Bronchospasm; hospitalization indicated for clinical sequelae; intravenous intervention indicated	Life-threatening consequences; urgent intervention indicated	Death
Definition: A disorder characterized by an adverse local or general response from exposure to an allergen.					
Anaphylaxis	-	-	Symptomatic bronchospasm, with or without urticaria; parenteral intervention indicated; allergy-related edema/angioedema; hypotension	Life-threatening consequences; urgent intervention indicated	Death
Definition: A disorder characterized by an acute inflammatory reaction resulting from the release of histamine and histamine-like substances from mast cells, causing a hypersensitivity immune response. Clinically, it presents with breathing difficulty, dizziness, hypotension, cyanosis and loss of consciousness and may lead to death.					
Autoimmune disorder	Asymptomatic; serologic or other evidence of autoimmune reaction, with normal organ function; intervention not indicated	Evidence of autoimmune reaction involving a non-essential organ or function (e.g., hypothyroidism)	Autoimmune reactions involving major organ (e.g., colitis, anemia, myocarditis, kidney)	Life-threatening consequences; urgent intervention indicated	Death
Definition: A disorder characterized by loss of function or tissue destruction of an organ or multiple organs, arising from humoral or cellular immune responses of the individual to his own tissue constituents.					
Cytokine release syndrome	Fever with or without constitutional symptoms	Hypotension responding to fluids; hypoxia responding to <40% O 2	Hypotension managed with one pressor; hypoxia requiring ≥ 40% O 2	Life-threatening consequences; pressor or ventilatory support indicated	Death
Definition: A disorder characterized by fever, tachypnea, headache, tachycardia, hypotension, rash, and/or hypoxia caused by the release of cytokines.					
Serum sickness	Asymptomatic; clinical or diagnostic observations only; intervention not indicated	Moderate arthralgia; fever, rash, urticaria, antihistamines indicated	Severe arthralgia or arthritis; extensive rash; steroids or iv fluids indicated	Life-threatening consequences; pressor or ventilatory support indicated	Death

Definition: disorder characterized by a delayed-type hypersensitivity reaction to foreign proteins derived from an animal serum. It occurs approximately six to twenty-one days following the administration of the foreign antigen. Symptoms include fever, arthralgias, myalgias, skin eruptions, lymphadenopathy, chest marked discomfort and dyspnea.

CTCAE= common terminology criteria for adverse events; iv= intravenous

Depending on the observed grade of reaction, respective measures like general and specific drug treatment (e.g., anti-histamines) as well as temporary or permanent stop of study drug administration in the affected participant will be applied. In case of a mild (grade 1-2 according to CTCAE v5.0) hypersensitivity reaction and an apparent symptoms relief, the

investigator may decide to cautiously continue further dosing. If any hypersensitivity symptom re-occurs dosing will be stopped permanently.

In case of hypersensitivity reactions of  $\geq 3$  dosing will be directly stopped permanently.

Anaphylaxis is strongly suspected when respiratory symptoms or hypotension occurs within 10 minutes of injection. All measures at site will be performed according the S2 Guideline for acute therapy and management of anaphylaxis (31).

### **8.3.9 AEs Requiring Submission to the CIAC**

All deaths, and events suspected to be related to cardiovascular disease, or other arterial or venous thrombosis (including AV access thrombosis), but not limited to these and starting after signing informed consent (randomized participants only), will be submitted to the CIAC for adjudication. Similarly, all bleeding events in randomized participants (except a participant's normal/expected post-dialysis bleeding from AV access) will be submitted to the CIAC for adjudication. Details of the adjudication process will be described in the adjudication charter and additional study specific guidance documents.

## **8.4 Treatment of Overdose**

In the event of an overdose, the investigator should:

1. Contact the Medical Monitor immediately.
2. Closely monitor the participant for any AE/SAE and laboratory abnormalities until study intervention can no longer be detected systemically (approx. 5 months).
3. Obtain blood samples for PK/PD analysis within 4 to 10 days and an additional one around 30 days from the date of the last dose of study intervention if not already scheduled according to the study protocol.
4. Document the quantity of the excess dose as well as the duration of the overdose in the eCRF.

Decisions regarding dose interruptions or modifications will be made by the investigator in consultation with the Medical Monitor based on the clinical evaluation of the participant.

## **8.5 Pharmacokinetics**

For the investigation of systemic exposure of osocimab and its relationship with treatment effects, the plasma concentrations of osocimab will be determined at different time points using a sparse sampling approach in all participating subjects. Details about the collection, processing, storage and shipment of samples will be provided separately (e.g., in the laboratory manual). Analysis of samples from participants not treated with osocimab is optional.

Blood samples will be collected at the time points indicated in the SoA (Section 1.3). PK samples obtained at additional time points based on the investigator's discretion will not qualify as a protocol deviation and will be used for PK analysis as well. Deviations from the specified time points will be documented and taken into account for the PK analysis. Date and time of the PK sample collection and date and time of most recent study drug administration must be documented accurately in the eCRF.

PK samples will be analyzed, using validated analytical methods. Quality control (QC) and calibration samples will be analyzed concurrently with study samples. The results of

calibration samples and QC samples will be reported in the Bioanalytical Report which will be included in the clinical study report (CSR) for this study.

Pharmacokinetic and exposure-response analysis might be performed using population approaches (popPK and popPK/PD, e.g., by non-linear mixed effect modeling). Analysis and report will be done under separate cover (see Section 6.3).

Exploratory analysis of unbound osocimab or of the complex of osocimab bound to FXI(a) might be done if applicable.

## 8.6 Pharmacodynamics

For the investigation of the pharmacodynamic response to osocimab and its relationship with treatment effects, pharmacodynamic parameters detailed below will be determined at different time points using a sparse sampling approach in all participating subjects. Details about the collection, processing, storage and shipment of samples will be provided separately (e.g., in the laboratory manual). Samples from participants not treated with osocimab will also be analyzed.

Blood samples will be collected at the time points indicated in the SoA (Section 1.3). Blood samples obtained at additional time points based on the investigator's discretion will not qualify as a protocol deviation and will be used for the PD analysis as well. Deviations from the specified time points will be documented and taken into account for the PD analysis. Date and time of the PD sample collection and date and time of most recent study drug administration must be documented accurately in the eCRF.

For PD evaluation of osocimab the last sample taken prior to first drug administration will be defined as reference time point (i.e., will be assigned to a relative time of 00d00h00m).

The actual date and time of blood sampling will be collected in the eCRF. All PD parameters will be measured using validated methods. Quality control and calibration samples will be analyzed concurrently with study samples. For selected parameters, results of QC samples will be reported together with analyte concentrations in the Clinical Study Report (CSR) for this study. Concentrations of the analyte are calculated according to the method description. Detailed method descriptions of all PD methods will be filed with the CSR for this study.

The following parameters will be used to assess the PD effects after administration of the investigational drug:

Main pharmacodynamic parameters:

- aPTT will be measured via the kaolin-trigger method (clotting assay). Furthermore, the aPTT assay will be conducted after in vitro-neutralization of heparin in order to separate potential heparin effects from the PD effect of osocimab.
- Factor XI activity will be assessed with an aPTT-based coagulation test using FXI deficient plasma. Furthermore, the assay will be conducted after in vitro-neutralization of heparin in order to separate potential heparin effects from the PD effect of osocimab.

Other pharmacodynamic parameters:

- Activated Factor XIa activity (AXIA) will be analyzed using a kaolin-trigger and a fluorogenic substrate readout.

- Factor XI concentration will be analyzed using an enzyme-linked immunosorbent assay (ELISA).
- D-dimer will be analyzed using a particle-enhanced immunoturbidimetric method.
- TAT (thrombin-antithrombin complex) will be analyzed using ELISA.
- F1.2 will be analyzed using ELISA.

The study sponsors reserve the right not to conduct all or part of the above-mentioned analysis.

## 8.7 Genetics

Genetic as well as non-genetic analyses may be part of the biomarker investigations in this study. Genetic investigations may be of any kind, except for whole genome sequencing. See Section 8.8 for details.

## 8.8 Biomarkers

Genetic as well as non-genetic biomarkers will be investigated. Biomarker analyses might be performed optionally and/or only in a subset of participants.

**Exploratory biomarkers:** FVIII activity, FIX activity, FXII activity, von Willebrand factor antigen level, ristocetin cofactor (i.e. von Willebrand factor) activity.

Furthermore, some PD markers listed under Section 8.6 might also be analyzed using alternative reagent/analyzer manufacturers in order to assess potential systematic influences of the analysis technology.

In addition to the biomarkers described above, further biomarkers related to, e.g., the mode of action or the safety of the study intervention and similar drugs may be investigated. The same applies to further biomarkers deemed relevant to cardiovascular and renal diseases and associated health problems. These investigations may include e.g., diagnostic, safety, pharmacodynamic, monitoring, or potentially predictive biomarkers.

### Timing

See SoA (Section 1.3) for planned time points of sample collection.

### Sample handling and storage

Details on the collection, processing, storage, and shipment of biomarker samples will be provided in separate documents (e.g., sample handling sheets or laboratory manual). Samples may be stored for a maximum of 15 years (or according to local regulations) following the end of the study at a facility selected by the sponsor to enable further analyses.

### Reporting

Some of the results of biomarker investigations may be reported separately (e.g., in a biomarker evaluation report).

## 8.9 Immunogenicity Assessments

The development of anti-drug antibodies (ADAs) to osocimab will be investigated in plasma samples from all participants taken at the time points indicated in the SoA (Section 1.3). Measurement of ADAs will be done batch-wise only as there is no expected direct impact on

participants' safety in this respective study setting. In case of any hypersensitive AE of life-threatening consequences the ADA measurement will be carried out at short notice.

Plasma samples will be screened for ADAs to osocimab and the result as well as the titer of confirmed positive ADA samples will be reported. ADA positive samples will be further characterized for their ability to neutralize the activity of osocimab (i.e. Neutralizing antibody (NAB) analysis). Other analyses may be performed to further characterize the immunogenicity of osocimab. Analysis of samples from participants not treated with osocimab is optional.

Further details on collection, labeling, storage, and shipping of samples are provided in a separate laboratory manual. Immunogenicity samples will be analyzed using validated analytical methods. Positive controls will be analyzed concurrently with study samples. The results of samples and positive control samples will be reported in the Bioanalytical Report which will be included in the CSR for this study.

## **8.10 Health Economics OR Medical Resource Utilization and Health Economics**

Health Economics/Medical Resource Utilization and Health Economics parameters are not evaluated in this study.

## **9. Statistical Considerations**

### **9.1 Statistical Hypotheses**

The primary objective of this study is a qualitative assessment of safety. All analyses are performed in a descriptive manner and thus no formal hypothesis is defined.

### **9.2 Sample Size Determination**

Assuming 25% screen failure proportion as based on historic operational experience, approximately 800 participants will be screened to achieve an estimated total of approximately 600 participants randomly assigned to study intervention. Of those, 555 participants are expected to complete the main treatment period assuming a true incidence rate of 15 participants with LTFU (lost to follow-up) (including e.g., withdrawal of consent) per 100 participant-years across all groups.

As a participant will be evaluated once he was randomized and received at least one dose of study intervention, the number of evaluable and randomized participants can be assumed to be similar.

In case that the observed overall incidence rate of participants with LTFU after the 400th participant is significantly higher than expected, the number of randomized participants may be increased (max. of 750 participants) to ensure a sufficient number of participants completing the main treatment period.

As all analyses will be performed in a descriptive manner, no statistically driven sample size calculation was performed.

The expected 90% confidence interval for the hazard ratio of the primary safety outcome is given by [0.57; 2.28], assuming

1. a true incidence rate of 10 participants with a major or clinically-relevant non-major bleeding event (in alignment with ISTH guidelines) per 100 participant-years in the placebo group (see below for definition)
2. a true hazard ratio of 1.0 (i.e. no change in relative risk) in both osocimab groups as compared to placebo
3. 6 months of treatment with a true incidence rate of 15 participants with LTFU per 100 participant-years across all groups.

The corresponding expected 90% confidence interval for the hazard ratio of the primary efficacy outcome is given by [0.44; 1.53]. while additionally assuming

1. a true incidence rate of 13 participants with a primary efficacy outcome per 100 participant-years in the placebo group.
2. a true hazard ratio of 0.75 in both osocimab groups as compared to placebo

For details on screen failures see Section 5.4.

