**Variable:**

- a. Time from first dose of intervention to treatment emergent major and clinically-relevant non-major bleeding events (in alignment with ISTH guidelines) up until 30 days after last study intervention
- b. Time from first dose of intervention to moderate or severe AEs and SAEs up until 30 days after last study intervention

**Treatment:** Low/high-dose osocimab or matching placebo on top of standard of care

**Intercurrent events:** Of interest is the response to treatment while the participant is

- alive (intercurrent event “death”) and
- exposed to study intervention ( intercurrent event “premature discontinuation of treatment”),

i.e. both intercurrent events are handled using the same strategy “while alive” or “while on treatment”.

**Population-level summary:** Hazard ratios comparing each of the osocimab dose groups with the placebo group as estimated from Cox proportional hazards models.

Please refer to Section 9.4 for further details.

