## 4. Study Design

### 4.1 Overall Design

Study 20115 is a covariate-adaptive randomization, double-blind, parallel group, placebo-controlled, multi-center study to assess the safety and tolerability of monthly administrations of a low and high dose cohort of osocimab given subcutaneously in ESRD patients on hemodialysis. In this protocol, the term hemodialysis includes hemodiafiltration. The overall study design is depicted in [Figure 1–1](#).

Approximately 600 participants (up to 750) from approximately 150 sites are planned to be randomized and will receive either osocimab (200 participants on each dose arm), or placebo (200 participants, i.e. 100 participants receiving low dose volume placebo and 100 participants receiving high dose volume placebo).

The following regions are planned to be included: North America, Europe, Asia Pacific.

The planned study will consist of:

- **Screening period (visit 1):** up to 14 days
- **Randomization (visit 2):** 1 day
- **Pre-treatment period (from visit 2 until visit 4):** 7 days
- **Main treatment period (from visit 5 until EOMT visit):** 6 months
- **Extension treatment period (from visit 19 until EOET visit):** up to 12 months
- **Follow-up period (from visit 32 until visit 35):** 4 months after end of treatment (EOMT or EOET)

Informed consent form will be obtained at the beginning of the screening period. During the screening period, participant's eligibility evaluations will be performed. Participants will be randomized either to osocimab or to placebo using a covariate-adaptive randomization technique (minimization methods) (for details see Section 6.3).

During the pre-treatment period, which will serve as a baseline period, a series of 3 hemodialysis sessions will be performed. Unfractionated or low molecular weight heparin (UFH/LMWH) is allowed as anticoagulation for maintenance of hemodialysis treatment during the whole study duration.

The study intervention will be administered subcutaneously abdominal with one single loading dose at visit 5 and monthly maintenance doses from visit 8 onwards until the end of the extension treatment period with an overall maximum of 18 months of treatment. The main treatment period consists of 6 months of treatment as this time frame is deemed to be the minimum clinically relevant treatment time to assess osocimab as chronic life-time treatment in an appropriate manner and in preparation for Phase 3.

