#### 9.4.1 General Considerations

The statistical analysis will be performed using SAS; the version used will be specified in the statistical analysis plan. In general, all variables including demography and baseline characteristics will be summarized by treatment group and by providing frequency tables for categorical variables and summary statistics for continuous variables.

For the primary analysis, only the main treatment period will be considered. The partial data of a participant's extended treatment period up until primary completion may be presented in separate tables. Furthermore, the primary analysis will be performed on the safety analysis set in accordance with the "population" attribute of the primary estimand.

In general, participants receiving placebo in either the low-dose or the high-dose cohort will be analyzed in a pooled manner. This group will be referred to as placebo group. The group of participants receiving osocimab in the high dose cohort (or low dose cohort) will be referred to as high dose (or low dose osocimab) group.

Where appropriate, the osocimab groups will be additionally displayed in a pooled manner.

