#### **9.4.2 Primary Endpoints**

The primary safety analysis is a descriptive time to first primary safety event (for both endpoints: composite of major and clinically-relevant non-major bleeding events [in alignment with ISTH guidelines] and moderate and severe AEs and SAEs).

The primary objective is to assess the safety under an osocimab concentration which is expected to be maintained during a chronic treatment. Thus the aim is to assess the response to treatment while the participant is

- alive (intercurrent event "death") and
- exposed to study intervention (intercurrent event "premature discontinuation of treatment").

Therefore, the time to the first primary safety event is defined as time from first dose of study intervention to the first event of the endpoint of interest up until 30 days after last study intervention in the main treatment period. The time under risk for a participant without a primary safety event will be censored at the date of the EOMT visit, or 30 days after study intervention discontinuation, or at the last date data was collected for a participant (e.g., for participants lost to follow-up) in the main treatment period, whatever occurs first.

The cumulative incidence risk for the primary safety event together with its confidence interval will be estimated. Each of the osocimab groups will be compared to the placebo group using two-sided log-rank tests at a type I error rate of  $\alpha=10\%$ . Due to the explorative nature of these analyses, no multiplicity adjustment will be done.

Hazard ratios comparing each of the osocimab groups with the placebo group and corresponding 90% (and 95%) confidence intervals will be estimated, as appropriate, from Cox proportional hazards models.

Hazard ratio, relative risk reduction (RRR;  $RRR = 100 \times [1 - \text{hazard ratio}]%$ ), and corresponding 2-sided 90% and 95% confidence intervals comparing each of the osocimab groups with the placebo group will be estimated based on two separate Cox proportional hazards models. Censoring will be assumed independent of the randomized group assignment.

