In addition, the primary safety and efficacy variables will be analysed descriptively for the following groups:

- each osocimab group, placebo high dose group, placebo low dose group,
- pooled osocimab group, pooled placebo group.

For the primary analysis and all analyses conducted at primary completion which will occur once the last patient completed the end of main treatment phase visit, only the main treatment period will be considered. The partial data of a subject’s extended treatment period up until primary completion may be presented in separate tables.

At full study completion, also the extension treatment and follow-up period will be considered.

Incidence rates and cumulative incidences will be calculated only for endpoints with at least 3 events in at least one treatment arm. Hazard ratios (cause specific and subdistribution) will be calculated only if in addition at least 1 event in each of the compared treatment arm occur.

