Cause-specific hazard ratios, cause-specific relative hazard reduction (csRHR; $csRHR = 100 \times [1 - \text{cause-specific hazard ratio}]\%$), and corresponding 2-sided 90% and 95% confidence intervals, comparing the hazards for the event-of-interest in each of the osocimab groups with the placebo group will be estimated based on two separate cause-specific Cox proportional hazards models. Censoring will be assumed independent of the randomized group assignment.

To complete the analysis, cause-specific HRs will be estimated for (each of) the competing events.

For the analysis of the primary endpoint in this study, the cause-specific hazard function $h_k(t)$ is the chance that an individual experiences an event of the primary safety outcome in the next instant in time, given that the individual has not had such an event or a competing event up to time t. For example, for the comparison of the osocimab high dose group with the placebo group, the corresponding cause-specific Cox proportional hazards model can be described by the following equation:

$$H_k(t, x_i) = h_{0,k}(t) \exp(\beta_k x_i),$$

where

$h_k(\cdot)$ cause-specific hazard function for primary safety outcome, as a function of time and subject's covariates

$h_{0,k}(\cdot)$ unspecified underlying baseline hazard function for primary safety outcome; hazard of an individual with $x_i = 0$

t time (in days) relative to the date of first administration

x_i	treatment group of subject i (0 corresponds to “placebo group” and 1 corresponds to “osocimab high dose group”)
β_k	unknown parameter (to be estimated); cause-specific hazard ratio = $\exp(\beta_k)$
k	type of event

Probability

As a supportive analysis, the cumulative incidence functions for the respective event-of-interest will be compared using the Fine and Grays subdistribution hazards model as well as using the Gray’s test.

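### The expected 90% intervals in Protocol 9.2 and SAP 9.1 name neither comparison nor method; they fit pooled osocimab against placebo and are too narrow for the per-dose primary comparison

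*Protocol*

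**What the plan says.** Protocol 9.2 gives two planning intervals: "The expected 90% confidence interval for the hazard ratio of the primary safety outcome is given by [0.57; 2.28], assuming" a placebo bleeding rate of 10 per 100 participant-years, a hazard ratio of 1.0 for both dose groups, and six months of treatment with loss to follow-up of 15 per 100 participant-years; and "The corresponding expected 90% confidence interval for the hazard ratio of the primary efficacy outcome is given by [0.44; 1.53"], adding a placebo rate of 13 per 100 participant-years and a hazard ratio of 0.75. SAP 9.1 repeats both. Neither section gives the groups compared, the group sizes, the event counts or the method.

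The primary comparison is clear elsewhere. The primary estimand in Protocol 3 is summarised by "Hazard ratios comparing each of the osocimab dose groups with the placebo group as estimated from Cox proportional hazards models". Protocol 9.4.2 repeats this ("Hazard ratios comparing each of the osocimab groups with the placebo group"), and SAP 6.4.1 says the hazards "in each of the osocimab groups with the placebo group will be estimated based on two separate cause-specific Cox proportional hazards models". The pooled-osocimab comparison is secondary to that: "Where appropriate, the osocimab groups will be additionally displayed in a pooled manner" in Protocol 9.4.1, and an additional descriptive grouping ("pooled osocimab group, pooled placebo group") in SAP section 6.

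**The concern.** The trial tests no formal hypothesis and makes no power statement, so these two intervals are the only statement of what about 600 participants can show. A reader would naturally take them as the precision of the primary hazard ratios, one per dose. If they describe pooled osocimab against placebo, they rest on twice as many treated participants as either primary comparison has. Each per-dose hazard ratio would then be less precise than the plan suggests. In a safety trial, that bears on how large an increase in bleeding the data could leave unexcluded.

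**Working it through.** **Inputs.** Rates, hazard ratios, six months and loss to follow-up are from Protocol 9.2. Group sizes are from Protocol 4.1 (participants "will receive either osocimab (200 participants on each dose arm), or placebo (200 participants"), with placebo pooled under Protocol 9.4.1. Intervals are two-sided 90%, z = 1.645.

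**Step 1: the basis of 9.2.** The completer figure reproduces as 600 × (1 − 0.15 × 0.5) = 555, so the section is built on 600 participants.

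**Step 2: what the stated intervals imply.** SE = ln(upper/lower) / (2 × 1.645); centre = √(lower × upper).
- Safety: ln(2.28/0.57)/3.29 = 0.421; centre √(0.57 × 2.28) = 1.14.
- Efficacy: ln(1.53/0.44)/3.29 = 0.379; centre √(0.44 × 1.53) = 0.82.

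The centres are not the assumed 1.0 and 0.75, so these are not closed-form intervals. An upward shift is what averaging over simulated trials with few events produces.

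**Step 3: expected events.** Events = n × λ/(λ + 0.15) × [1 − exp(−(λ + 0.15) × 0.5)].
- Safety, λ = 0.10, n = 200: 80 × 0.1175 = 9.40 per group; 18.8 in 400 on osocimab.
- Efficacy, placebo, λ = 0.13, n = 200: 92.86 × 0.1306 = 12.13.
- Efficacy, one dose, λ = 0.0975, n = 200: 78.79 × 0.1164 = 9.17; 18.3 in 400 on osocimab.

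**Step 4: closed form.** Limits = HR × exp(±1.645 × √(1/e₀ + 1/e₁)).
- Per dose, safety: SE √(1/9.40 + 1/9.40) = 0.461, giving [0.468; 2.136].
- Per dose, efficacy: SE √(1/12.13 + 1/9.17) = 0.438, giving [0.365; 1.540].
- Pooled osocimab: [0.52; 1.93] and [0.41; 1.38].

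The stated SEs are about 9% (0.421 v 0.461) and 13% (0.379 v 0.438) too small for the per-dose comparison. An SE of 0.421 would need 2/0.421² ≈ 11.3 safety events per group.

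**Step 5: averaged simulated limits.** Event and loss times were exponential with a six-month cut-off. Each 200 v 200 and 400 v 200 scenario used 120,000 trials with a rate-ratio estimator, checked by 6,000 Cox fits (in brackets). Rates were either taken as hazards or converted as −ln(1 − rate).

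| Comparison | Safety | Efficacy |
|---|---|---|
| Stated | 0.57; 2.28 | 0.44; 1.53 |
| 400 v 200, converted | 0.565; 2.298 (0.563; 2.283) | 0.440; 1.525 (0.443; 1.537) |
| 400 v 200, hazards | 0.557; 2.363 (0.554; 2.329) | 0.433; 1.572 (0.437; 1.597) |
| 200 v 200, converted | 0.517; 2.524 (0.513; 2.526) | 0.401; 1.699 (0.399; 1.705) |
| 200 v 200, hazards | 0.510; 2.607 (0.510; 2.595) | 0.391; 1.748 (0.391; 1.743) |
| 250 v 250, converted | 0.552; 2.213 | 0.425; 1.527 |

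In a separate set of 8,000 Cox fits with rates as hazards, the mean SEs were 0.416 and 0.381 for 400 v 200, close to the implied 0.421 and 0.379. For 200 v 200 they were 0.487 and 0.458. Using mean HR × exp(±1.645 × mean SE), 400 v 200 gives [0.572; 2.250] and [0.438; 1.535].

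**Step 6: simulation error.** If the planning run used 1,000 trials (an assumption), the 95% Monte Carlo ranges of the averaged limits, with rates as hazards, are:
- 400 v 200: safety 0.544–0.570 and 2.244–2.451; efficacy 0.423–0.443 and 1.517–1.615. All four stated limits fall inside.
- 200 v 200: safety 0.491–0.523 and 2.495–2.758; efficacy 0.383–0.407 and 1.709–1.818. None does.

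**The case against.** **The pooled origin is not documented.** The hazard ratios in 9.2 are assumed for both dose groups against placebo, which can be read as per-dose language. The close match by averaged limits needs converted rates; with rates as hazards it relies on Monte Carlo error from an assumed run size. This stands: the origin is an inference. The shortfall in per-dose precision does not rest on it, because at 200 v 200 under the stated assumptions both the closed-form and the simulated SEs exceed the implied ones.

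**A per-dose setting comes near.** Section 9.2 allows up to 750 participants, about 250 v 250. With rates as hazards, averaged limits there are [0.546; 2.280] and [0.420; 1.576]. The safety upper limit fits, but both lower limits and the efficacy upper limit miss. With converted rates the efficacy upper limit fits, but the lower limits still fall short. Section 9.2 is also built on 600.

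**The limit that matters for bleeding is not overstated in closed form.** The closed-form per-dose upper limit is 2.14, below the stated 2.28; for efficacy it is 1.54 against 1.53. This stands: on that method only the lower limits are materially too favourable, although the safety interval is still too narrow as a ratio (4.6 against 4.0).

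**The consequence is small.** The documents say the sample size was not derived statistically, no decision rests on these intervals, and SAP 6.5 indicates that the primary analysis was already complete. This limits the weight of the point. It does not make an unlabelled precision figure correct.

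**Conclusion.** The point holds. For the comparison the plan defines as primary, the stated intervals are too narrow on the log scale whether closed form or simulation is used.

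By averaged simulated limits, the per-dose safety interval is about [0.51–0.52; 2.5–2.6] against [0.57; 2.28], an upper-to-lower ratio of 4.9–5.1 against 4.0. The efficacy interval is about [0.39–0.40; 1.70–1.75] against [0.44; 1.53], a ratio of 4.2–4.5 against 3.5. The spread reflects whether rates are converted or taken as hazards. These sizes assume exponential event and loss times, exactly six months at risk and 200 per group. Pooled osocimab against placebo is the best explanation found for the stated figures, but only the sponsor can confirm it. The plan should be corrected; the design is not affected.

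**What to change.** In Protocol 9.2 and SAP 9.1:

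1. State how the expected interval was obtained (averaged simulated limits or closed form), with the group sizes, expected event counts and whether rates were taken as hazards or converted.
2. Label [0.57; 2.28] and [0.44; 1.53] as pooled osocimab against placebo, if the sponsor confirms that this is what they are.
3. Add the interval for each dose against pooled placebo (200 v 200), by the same method and rate convention, as the precision of the primary comparison. With averaged limits this is about [0.51; 2.6] and [0.39; 1.75] with rates as hazards, or [0.52; 2.52] and [0.40; 1.70] with converted rates. In closed form it is [0.47; 2.14] and [0.37; 1.54].

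The cost is wording in two sections and a slightly less favourable precision statement. Enrolment, conduct and analysis do not change. If the documents can no longer be amended, the same clarification belongs in the study report.
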